5.3 Randomization

Random permuted blocks with a fixed size of 3 will be used for randomization into treatment groups. We will stratify participants based on open vs. closed loop insulin pump use and age prior to randomization.

5.4 Participant Compensation

Research subjects will be compensated for their time and inconvenience in the study in the form money in the amounts specified below. Following study completion, participants will be mailed a check equal to the dollar amount below.

- Visit 1 (Screening visit): the initial screening visit will last approximately 2-3 hours. Subjects who complete their screening visit will be compensated \$25.
- Visit 2 (Week 1 visit): this visit will last approximately 2-3 hours. Subjects who complete this week 1 visit will be compensated \$25.
- Visit 3 (Week 12 visit): this visit will last approximately 1-2 hours. Subjects who complete this week 12 visit will be compensated \$25.
- Telephone visits (weeks 2, 4, 8): these visits will last approximately 30-60 minutes. Subjects who complete these visits will be compensated \$10 per visit.
- Participants will receive full compensation for study visits and telephone visits only if they have completed all pre-visit tasks, which will be outlined in both the consent documentation and included in the written instructions participants are given in the preceding visit.

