6.1.1.6 Randomization

We will then randomize patients to 1 of 3 groups: group 1 is low carbohydrate diet, group 2 is standard carbohydrate diet, group 3 is general diabetes education without dietary recommendation. Each group will contain 15 participants. Random permuted blocks with a fixed size of 3 will be used for randomization into treatment groups.

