10.0 Statistical Considerations

10.1 Recruitment and Sample Size Justification

We have targeted an accrual of 40 participants in this pilot study to achieve two goals. First, we require a sufficient number of participants to estimate the effect size and variance of the LCD as a means to reduce HbA1c in T1DM in a future definitive trial. We utilized the method of Whitehead et al. to estimate our pilot study's optimum accrual, which proposes stepped increases in sample size based on the anticipated standard difference, d, between interventions 41,42 . We defined the minimum important difference (MID) in Δ HbA1c between LCD and SCD interventions as 0.3% and estimated a pooled SD of 0.8% based on our literature review9. If d=MID/SDpooled=0.3%/0.8%=0.38, a sample size of 20 participants per arm will optimize future sample size calculations for the definitive study, while allowing for up to 40% dropout. Second, this sample size allows for up to 4 degrees of freedom in multivariable linear regression analysis.

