10.2 Statistical Analysis

Statistical analysis will be performed using an independent samples t-test to compare change from baseline to 3 months post-intervention values from each aim (Δ HbA1c, Δ LDL-P, and Δ QOL score) between the two groups. We will also perform a series of multivariable linear regression analyses with change in primary outcomes from each aim (Δ HbA1c, Δ LDL-P, and Δ QOL score) from baseline to 12 weeks post-intervention as the dependent variable. Explanatory variables in the multivariable linear regression modeling will include mean total daily dose of insulin normalized for body mass, weight change, coefficient of variation of glucose as measured by CGM, and age.

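### Loop type and age stratify the randomisation, but the t-test uses neither and the regression leaves out loop type; if they predict the change score, reported precision is understated

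*Combined protocol and SAP*

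**What the plan says.** Section 5.3 (Randomization) names two stratification factors: "We will stratify participants based on open vs. closed loop insulin pump use and age prior to randomization". It gives no age cut-points. Section 6.1.1.6, the visit-level description, repeats the blocking rule without the strata: "Random permuted blocks with a fixed size of 3 will be used for randomization into treatment groups".

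Section 10.2 plans two analyses. The first is unadjusted: "Statistical analysis will be performed using an independent samples t-test to compare change from baseline to 3 months post-intervention values from each aim". The second is a set of multivariable regressions on the change scores, with these explanatory variables: "mean total daily dose of insulin normalized for body mass, weight change, coefficient of variation of glucose as measured by CGM, and age". Age is therefore in the regression, loop type is in neither analysis, and the list does not name a group term. The plan gives no stratified test, no stratum term and no reason for leaving them out.

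Section 10.1 says that "this sample size allows for up to 4 degrees of freedom in multivariable linear regression analysis". It states that the pilot is meant to supply the effect size and variance for a definitive trial, and it allows for dropout of up to 40%.

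**The concern.** Blocking within strata makes the arms alike on the stratification factors. If a factor predicts the outcome, the variation that it causes largely drops out of the difference between arms. An analysis without the factor still counts that variation as residual noise. The estimated difference is then more precise than its standard error says: the interval is too wide and the test rejects less often than its nominal level.

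With about 15 participants per arm, precision is scarce, and the estimate and its interval are the main product of this pilot. Both factors are known before allocation, so using them costs very little.

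**Working it through.** **Inputs from the documents.** Section 10.1 gives a minimum important difference "between LCD and SCD interventions as 0.3" percentage points of HbA1c and "estimated a pooled SD of 0.8". Sections 2.0 and 6.1.1.6 give 15 per group; Section 10.1 gives 20 per arm. Both sizes are shown.

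**Assumptions.** A two-sided 5% level (none is stated). R² is the share of change-score variance explained by the stratification factors; the documents give no value, so a range from 0 to 30% is used. Age is taken as two strata.

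**The plan's own figure.** d = 0.3/0.8 = 0.375, which matches the stated 0.38. The step from d to 20 per arm rests on a cited rule that the documents do not reproduce, so it can be neither confirmed nor refuted. The present point does not depend on it.

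**Interval width, no losses.**
- Unadjusted: SE = SD × √(2/n) = 0.8 × √(2/15) = 0.292. Half-width = 2.048 × 0.292 = 0.598 (28 df).
- Adjusted for loop type and age: half-width = 2.056 × 0.292 × √(1 − R²) (26 df).

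| R² | Adjusted half-width, 15 per arm | Unadjusted (0.598) relative to adjusted | Adjusted half-width, 20 per arm (unadjusted 0.512) |
|---|---|---|---|
| 0 | 0.600 | 0.3% narrower | 0.513 |
| 5% | 0.585 | 2% wider | 0.500 |
| 10% | 0.570 | 5% wider | 0.487 |
| 20% | 0.537 | 11% wider | 0.459 |
| 30% | 0.502 | 19% wider | 0.429 |

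**Type I error of the t-test, no losses.** With the factors balanced, the true SE is about √(1 − R²) times the reported one. The type I error is then about P(|t| > 2.048/√(1 − R²)) on 28 df:
- R² = 10%: P(|t| > 2.159) ≈ 4.0%
- R² = 20%: P(|t| > 2.290) ≈ 3.0%
- R² = 30%: P(|t| > 2.448) ≈ 2.1%

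Simulation of the actual scheme (45 randomised to three arms, blocks of three within four loop-by-age strata, LCD compared with SCD) agrees. It gave 4.3% at an R² of 10% and 2.8% at 20%. Adjusting for both factors brought the level back to about 5% in every setting.

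**Does age alone suffice?** No. With an R² of 20% split equally between the two factors, a model with arm and age only still has a type I error of 3.7% (reported SE 0.278, true SE 0.261).

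**With 40% random loss** (15 × 0.6 = 9 completers per arm). The balance partly erodes. In simulation the t-test's type I error was about 4.7%, 3.5% and 3.3% at an R² of 10%, 20% and 30% (Monte Carlo error about 0.2 points). Adjusting for both factors shortened the interval by about 0%, 7% and 13%, and lengthened it by about 4% at an R² of 0.

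**The case against.** The strongest reply is that the loss is conditional, conservative and possibly small. Section 10.2 analyses change from baseline, so it is not enough that loop type or age goes with a higher or lower HbA1c level; it must predict the change. No figure in the documents shows that it does. At an R² of up to 10% the cost is at most about 5% of interval width, and losses after randomisation shrink it further. The run-in exclusions at Visit 2 come after allocation and add to those losses. There is no bias and no excess of false positives, and the stated aims are preliminary estimates. All of this stands and limits the size of the point.

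A reader might infer that the stratification is wasted. It is not. At an R² of 20% the true SE is 0.262 against a reported 0.293, so the trial does gain the precision; the t-test just does not report it.

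A reader might also infer that the pilot SD will overstate what the definitive trial needs. That holds only if that trial adjusts for the strata: the excess in sample size would be 1/(1 − R²), or 1.11 at an R² of 10% and 1.25 at 20%. For an unadjusted trial the unadjusted SD is the right input, and the residual SD can in any case be computed later from the same data.

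Finally, a reader might take Section 6.1.1.6 to mean that strata may not be used at all. It only omits them. Section 5.3 is the dedicated section and is explicit.

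**Conclusion.** The mismatch between design and analysis is real: loop type enters no planned analysis, and age is missing from the t-test. If these factors predict change, the t-test is conservative and its interval too wide. With no losses, the type I error is about 4–4.5%, 3% and 2% and the excess width about 5%, 11% and 19%, at an R² of 10%, 20% and 30%. At an R² of 0 there is no loss, and at 40% dropout the effect is smaller throughout. The documents do not support an unconditional statement that the intervals are too wide.

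The figures rest on the SD of 0.8, a two-sided 5% level, an assumed R², strata split about evenly and, where dropout is modelled, losses at random. That both pump types are enrolled is inferred from Section 5.3, because the contents of the eligibility table are not in the text available for review. The case for change is that the remedy is nearly free, not that the planned test would mislead.

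**What to change.** - **Section 10.2.** Make the main LCD–SCD comparison a linear model of the change score on arm, loop type at randomisation and age, in place of the unadjusted t-test. Say whether age enters as the randomisation strata or as a continuous variable.
- **Section 10.2, further regressions.** Include loop type and name the arm term. The four listed covariates already fill the four degrees of freedom of Section 10.1, so the list and the budget must be reconciled. Three of the four (insulin dose, weight change, glucose variability) are not stated to be baseline values and may respond to the diet, so they are the natural ones to reconsider. The proposed main model has three terms if age is in two strata, which is within the budget.
- **Section 5.3.** State the age cut-points.
- **Section 6.1.1.6.** Say that the blocks are drawn within the Section 5.3 strata.

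**Cost.** Two degrees of freedom. If the factors prove non-prognostic, the interval widens by about 0.3% at 15 per arm, and by up to about 4% at 40% dropout. No new data are needed, since both factors are known at randomisation.

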6.0 Study Procedures

6.1 Research visits

[figure not shown]

Figure 1: Study Timeline

6.1.1 Study Visit 1, Initial Screening Visit (Week -2)

Screening visits will take place in a room designated for research in the Eskind Diabetes Center or the Vanderbilt Children's Endocrinology Franklin Clinic.

The purpose of the screening visit is to:

- obtain informed, written consent/assent,
- conduct a history and physical exam,
- confirm each participant is able to properly use their insulin pump and continuous glucose monitor (CGM),
- calculate the estimated energy requirement to be consumed before during the study period,
- show participants how to log their food intake on their digital device.

The screening visit will consist of the following:

6.1.1.1 Consent/Ascent

The PI or designated KSP will obtain consent/assent from all participants. Consent/assent will be obtained in a private room in the Eskind Diabetes Center or Vanderbilt Children's Endocrinology Franklin clinic prior to beginning study procedures. The consent and assent form will be provided to the subject and family (if applicable) for review prior to the visit. The PI or designated Key Study Personnel will review the consent/assent forms with the family in detail and

provide time for discussing any questions. The study team will provide a copy of the consent/assent form to the participant and parents if applicable.

6.1.1.2 History and Physical Exam

The PI or designee will review each subject's clinical history, perform a physical exam, and take anthropometric measurements.

6.1.1.3 Nutritional Tracking App Instructions

The study team will use a nutritional tracking smartphone application, such as Nutrihand, MyFitnessPal, or FatSecret, on which participants will log their daily caloric intake using the software's webbased or Smartphone app interfaces. Participants will be asked to intermittent track intake using this smartphone app throughout the study.

Participants may be asked to use their personal email to send a CSV file containing data files from the smartphone app to the study team. This CSV file does not contain any PHI. The file will be directly uploaded into REDCap, then the email will be permanent deleted.

6.1.1.4 Continuous Glucose Monitor Instructions

The study team will instruct T1DM participants in the use of a continuous glucose monitor (CGM) such as Dexcom G6 or Medtronic Guardian for the monitoring of glycemia during the study. The team will then show T1DM participants how to upload CGM data into a HIPAA and FDA-compliant cloud-based, data-integration platform such as Dexcom Clarity or Tidepool. The team will show the control participants how to use the CGM device during this time.

Participants in group 3 will also be asked to keep a manual blood glucose log intermittently throughout the study.

6.1.1.5 Insulin Pump Instructions

The study team will instruct T1DM participants in the use of an insulin pump such as Medtronic Minimed 670G, Tandem T-Slim, or Omnipod Insulim Management System for the administration of insulin during the study. Instructions will include administering all insulin via insulin pump and recording all carbohydrates consumed into the insulin pump. The

team will then show T1DM participants how to upload insulin pump data into a HIPAA and FDA-compliant cloud-based, data-integration platform such as Medtronic Careline or Tidepool. The team will show the control participants how to use the insulin pump device during this time.

6.1.1.6 Randomization

We will then randomize patients to 1 of 3 groups: group 1 is low carbohydrate diet, group 2 is standard carbohydrate diet, group 3 is general diabetes education without dietary recommendation. Each group will contain 15 participants. Random permuted blocks with a fixed size of 3 will be used for randomization into treatment groups.

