6.1.2 Run In Period (Weeks -2 to 0)

Participants will log all dietary intake in the smartphone nutritional tracking app, which will serve as a baseline of dietary habits. They will also be instructed to consistently wear the CGM and to administer insulin boluses using their pump's bolus calculator.

Participants in groups 1 and 2 will be asked to complete nutritional tracking in the smartphone app during this time. Participants in group 3 will be asked to complete a blood sugar and exercise log.

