6.1.3 Study Visit 2 (Week 0)

This visit will correspond with the participant's routine diabetes follow up at the Eskind Diabetes Center or Vanderbilt Children's Endocrinology Franklin clinic with their primary endocrinologist. Each T1DM participant's endocrinologist will manage his or her glycemic control and insulin doses throughout the study. The study team will review data from the nutrition log, CGM, and insulin pump. Participants will be excluded for any of the following:

- Tracking < 2 meals per day in the nutritional tracking app
- Entering carbohydrates from < 2 meals per day in their insulin pump
- Wearing CGM < 80% of run-in period.

6.1.3.1 History and Physical Exam

The PI or designee will review each subject's clinical history, perform a physical exam, and take anthropometric measurements. They will ensure the patient has an up to date intramuscular glucagon kit for treatment of hypoglycemia as needed.

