6.1.4.2 Text Messaging

Participants will receive text messages 2 to 4 times per week³⁶ that will provide reminders regarding key components of the dietary intervention, encouragement regarding diabetes management, and general positive quotes. The study team will create a bank of 50 text messages for each dietary intervention (LCD and SCD), and participants will receive 2 to 4 of these text messages per week. Examples of message content include: "Try a breakfast high in protein! An omelet with a side of bacon would be a great choice" and "The only way of finding limits of the possible is by going beyond them and into the impossible – Arthur C. Clarke." The text message will be sent using the text messaging feature in RedCap with the Twilio messaging service and will contain no protected health information. Text messaging will continue until participants have completed study visit 3.

6.1.5 Telephone Visits (Weeks 2, 4, and 8)

The study team will monitor adherence by reviewing each participant's dietary log, CGM data, and insulin pump data. The team will conduct a 30 to 60-minute telephone session (either via Facetime, Skype, or phone call) with the participant. The study team will review with the participants their nutritional intake and reinforce key concepts from the diet to which they are assigned (LCD or SCD). If the CGM is being worn less than 80% of the time or insulin pump is not being used to record more than 2 meals per day, the study team will troubleshoot the reason for suboptimal adherence with the participant.

Participants in groups 1 and 2 will be asked to complete nutritional tracking in the smartphone app during this time. Participants in group 3 will be asked to complete a blood sugar and exercise log.

In the event that study visit 3 occurs more than 14 weeks after study visit 2, we will conduct an additional telephone visit at week 12. We will

continue to conduct a telephone visit every 4 weeks after week 12 until the participant has completed study visit 3.

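### Randomisation at week -2 precedes a run-in whose compliance failures are excluded at week 0, with no analysis rule for them; group 3's app use in the run-in is also unclear

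*Combined protocol and SAP*

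**What the plan says.** All references are to the combined protocol and SAP.

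- **Allocation.** Section 6.1.1.6 closes Visit 1 (week -2) with "We will then randomize patients to 1 of 3 groups". Section 5.3 describes blocks and strata but gives no later time.
- **Run-in, weeks -2 to 0 (6.1.2).** The opening sentence covers everyone: "Participants will log all dietary intake in the smartphone nutritional tracking app". The second paragraph divides tasks by allocated group: "Participants in groups 1 and 2 will be asked to complete nutritional tracking in the smartphone app during this time", and "Participants in group 3 will be asked to complete a blood sugar and exercise log".
- **Week 0 (6.1.3).** "Participants will be excluded for any of the following". The criteria are "Tracking < 2 meals per day in the nutritional tracking app", pump carbohydrate entries from fewer than two meals per day, and CGM wear below 80% of the run-in. None is limited to particular groups.
- **Baseline.** HbA1c, lipoproteins and surveys are collected at this same visit (6.1.3.2, 6.1.3.5). The assigned diets run from week 0 (6.1.3.6).
- **Analysis.** Section 10.2 compares change scores between two groups and defines no analysis set. Section 10.1 allows up to 40% dropout without saying whether run-in exclusions count. The withdrawal reasons in section 9.0 do not mention run-in failure.

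**The concern.** A compliance filter is neutral by design only when it comes before allocation. Here it comes after, and staff are already using the allocation, because section 6.1.2 sets tasks by group number. The groups reaching week 0 are then no longer simply the randomised groups. If compliance is related to later HbA1c change and the losses differ by arm, the comparison is shifted. This pilot is meant to supply effect and variance estimates for a definitive trial (10.1), so a shift would carry forward.

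The missing rule matters more because exclusion and baseline measurement fall at the same visit. A participant excluded there may have no baseline value, and a change-score analysis could not recover that person later.

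The uncertainty over group 3 is a separate matter. Sections 2.0 and 6.1.3.6 rely on that group to separate the effect of diet composition from the effect of receiving any dietary prescription. If it passes through a different filter from the other two groups, that interpretation is weaker.

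**Working it through.** **1. Order of events.** Visit 1, week -2: randomise (6.1.1.6). Weeks -2 to 0: tasks by group (6.1.2). Week 0: exclude on run-in compliance (6.1.3), take baselines (6.1.3.2 to 6.1.3.5), give diet instruction (6.1.3.6). The exclusions therefore come after allocation but before the intervention.

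**2. Inputs.** From section 10.1: SD of HbA1c change 0.8%, minimum important difference (MID) 0.3%. From section 6.1.1.6: 15 per group. Section 10.1 works with 20 per arm; that mismatch is a separate matter. Assumed, because the documents give neither: run-in loss rates p, and the correlation r between run-in compliance and HbA1c change. No figure in the plan is disputed here, so there is none to reproduce.

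**3. LCD against SCD.** If the least compliant fraction p of an arm is removed, and compliance and HbA1c change are jointly normal, the mean change among those kept shifts by r × SD × φ(z_p)/(1 − p). Here z_p is the p-quantile of the standard normal and φ its density. The bias is the difference between the two arms' shifts.

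- Equal losses arising in the same way: the shifts cancel and the bias is 0.
- p = 0.10, r = 0.3: 0.3 × 0.8 × 0.1755/0.90 = 0.0468.
- p = 0.25, r = 0.3: 0.3 × 0.8 × 0.3178/0.75 = 0.1017.
- Difference: 0.1017 − 0.0468 = 0.055%, which is 0.055/0.3 = 18% of the MID.
- Loss pairs 10/20, 10/25, 15/25 and 5/25% with r from 0.1 to 0.5: 0.012% (15/25, r = 0.1) to 0.126% (5/25, r = 0.5).

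For scale, the 95% confidence interval half-width at 15 per arm is t(28) × 0.8 × √(2/15) = 2.048 × 0.292 = 0.60%. The central illustration is 0.055/0.598 = 9% of that, and the top of the range 0.126/0.598 = 21%. The direction is unknown, and the range reflects the assumptions and is not a bound.

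**4. Precision.** If 45 people enter the run-in and a fraction f fails, 45 × (1 − f) remain whether allocation came before or after. At f = 0.20 that is 36, or 12 per arm on average, with half-width 2.074 × 0.8 × √(2/12) = 0.68% under either order.

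**5. Does group 3 use the app in the run-in?**

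- For everyone using it: the opening sentence of 6.1.2; section 6.1.1.3 ("Participants will be asked to intermittent track intake using this smartphone app throughout the study"); section 6.1.3.4, which collects app data at week 0 with no group limit; and section 6.1.1.4, where the word also suggests that group 3's log is additional ("Participants in group 3 will also be asked to keep a manual blood glucose log intermittently throughout the study").
- For groups 1 and 2 only: the second paragraph of 6.1.2. The same sentence recurs in 6.1.5 and 6.1.6.4, but those sections cover later periods and cannot settle the run-in.

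On the broader reading all groups face three criteria. On the narrower reading, with the app criterion waived for group 3, that group faces two and the others three. Assume 10% lost to the shared criteria in every group and a further 5 to 25 percentage points lost in groups 1 and 2:

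- 15% against 10%, r = 0.1: 0.1 × 0.8 × (0.2743 − 0.1950) = 0.006%.
- 35% against 10%, r = 0.5: 0.5 × 0.8 × (0.5698 − 0.1950) = 0.15%.

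Section 10.2 tests no contrast with group 3, so these figures bear on interpretation only.

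**The case against.** The strongest reply is that nothing distinguishes the LCD and SCD arms before week 0. They have the same tasks and criteria, and diet instruction has not begun. HbA1c and LDL-P are laboratory measures, so taking them after allocation adds little. Any bias is conjectural and, on the figures tried, small beside the pilot's own uncertainty. That stands as a limit on the harm. It does not supply a rule for the excluded participants, and it would exclude differential loss only if participants did not know their arm during the run-in, which the protocol does not state.

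Three stronger inferences are tempting and are not supported:

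- *The LCD against SCD comparison is biased.* The documents show a route to bias, not its presence.
- *Early randomisation costs precision.* Step 4 shows that the loss comes from run-in failure itself. Randomising later restores 15 per arm only if more people are screened.
- *All of group 3 would be excluded.* That follows only from the narrower reading applied literally. It is implausible, because sections 2.0 and 6.1.3.6 require a group 3.

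It is also fair to say that analysing everyone as assigned does not settle how a change-score test treats a missing week-12 value. Section 10.2 needs to address that in any case.

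**Conclusion.** The sequencing fault and the missing analysis rule are clear from the current text: the plan as written removes randomised participants for behaviour after allocation. The harm is uncertain. For LCD against SCD it is zero if losses are equal and arise in the same way; otherwise the illustration is about 0.055% HbA1c, with 0.01% to 0.13% over the assumed losses and r of 0.1 to 0.5. The lack of clarity over group 3's app use is a wording fault. On the narrower reading, with the criterion waived, the illustrative shift in contrasts with that group is about 0.006% to 0.15%. Only the SD and MID come from the protocol; loss rates and correlations are assumptions. The point should be fixed because the remedy is cheap, not because a material bias has been shown.

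**What to change.** **Preferred.**

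- Move randomisation from section 6.1.1.6 to Visit 2, after the run-in review, baseline bloods, CGM download and surveys.
- Give all participants the same run-in tasks and criteria, reconciling 6.1.2 with 6.1.1.3, 6.1.3 and 6.1.3.4.
- Count run-in failures as unrandomised screen failures.
- State in section 10.2 that randomised participants are analysed in their assigned group.

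**If randomisation stays at Visit 1.** Keep every randomised participant in baseline measurement, outcome follow-up and analysis by assigned group, whatever their run-in compliance, and still clarify group 3's app use. The sponsor would need to reconcile the CGM-wear check in 6.1.3 with the safety provision in 7.1.2. Baselines would still follow allocation.

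**Cost of the preferred change.** A protocol amendment, and diet plans ready before the arm is known. Section 6.1.3.6 already calls for two plans per participant in groups 1 and 2, so this is new only for those later allocated to group 3. The sponsor then either accepts fewer randomised participants or screens more. At assumed run-in failure of 10% to 40%, 45/0.9 = 50 to 45/0.6 = 75 people are needed, or 5 to 30 extra. From section 5.4, at 2 to 3 hours and $25 per screening visit, that is 5 × 2 = 10 to 30 × 3 = 90 participant-hours and $125 to $750. Those who fail would also attend part of Visit 2 and might be owed some of its payment.
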